8.5.10 Reporting of Pregnancy

Pregnancy is not an AE. However, any pregnancy that occurs during study participation (through study Day 28) should be reported to the sponsor on the appropriate CRF. Pregnancy should be followed to outcome. This follow-up will include pregnancy outcome (termination, pre-term birth, term birth) and newborn outcome (live birth, fetal demise, stillbirth; presence of any congenital anomalies). No in-person visits will be required for pregnancy outcome determination.

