- On Day 7 EVENING DOSE: Within 30 min before the evening dose (t=0), and at 0.5h (± 5 min), 1h (± 5 min), 2h (± 5 min), and 4h (± 5 min) after the evening dose on Day 7.
- On Day 8: At 6h (± 10 min), 8h (± 10 min), 12h (± 15 min), and 24h (± 15 min) after the evening dose on Day 7.
- On Day 9: At 36h (± 15 min) and 48h (-2 hours) after the evening dose on Day 7.

(v) Participant counseled to avoid prohibited lifestyle activities and prescription and non-prescription medications and use recommended contraception methods after Screening and, if enrolled and dosed, for the duration of study. Before or at discharge from the in-patient phase on Day 9, participants must be counseled to use recommended contraception and avoid pregnancy for at least 30 days after the last study dose. Male participants must be counseled to avoid donating sperm for 30 days after the last dose received in the study.

(w) An unscheduled visit to the CTU may be initiated by study staff after each outpatient follow up by phone call for evaluation of any new AEs assessed as moderate or above or SAEs or AESIs by the study PI or authorized clinician. The evaluation will consist of a history of the AE, any ConMeds taken, focused PE and, as needed, clinical laboratory tests, ECG and other tests as indicated. Any ongoing AEs after discharge from the CTU on Day 9 may also be followed with as needed assessments during unscheduled visits.

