 - Note 3: Acceptable forms of primary contraception include a monogamous relationship with a vasectomized partner who has been vasectomized for 180 days or more before the participant receiving the study product, tubal ligation, non-hormonal intrauterine device, and if in a monogamous relationship with a male partner who uses a barrier method without spermicide.
 - Note 4: Specified periods include at least 30 days prior to screening, during the period between screening and completion of dosing, and until at least 30 days following receipt of the last dose of study product.
7. Women of childbearing potential must have a negative serum β -human chorionic gonadotropin (HCG) pregnancy test at screening and a negative urine HCG pregnancy test at check-in (Day-1) within 24 hours before receiving the initial study product.

8. Male participants receiving the study product must use acceptable contraception and refrain from donating sperm from the day of first dose until 30 days after the last dose or be vasectomized.¹
 - Note 1: Acceptable contraception includes abstinence from intercourse with a female of childbearing potential or use of a male condom without spermicide when engaging in any activity that allows for the passage of ejaculate to a female during the intervention period and for at least 30 days after ending study dosing, or surgical sterilization for 180 days or more.
9. Willing to avoid excessive physical exercise starting within 48 h prior to dosing and until discharge from the CTU on Day 9.
10. No history of acute febrile or infectious illness for at least 7 days prior to the administration of study drug.

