5.2.1 Exclusion of Specific Populations

Because the effects on the fetus are not known, pregnant women will not be eligible for the trial. Women of childbearing potential must utilize a highly effective method of contraception and will be required to have a negative urine pregnancy test on Check-in (Day -1) (within 24 h prior to initiation of study drug administration).

Children will not be included in this trial as presently there are no safety or efficacy data in adults. Should the outcome of this trial be deemed acceptable, additional trials may be initiated, including those in other populations.

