8.4 Study Drug Administration

Participants will receive daily dosing Q12h (morning and evening) for 7 days, with the first dose of the study drug administered in the morning on Day 1 and the last dose in the evening of Day 7. The study product will be administered orally with at least 240 mL (8 fluid ounces) or more of tap or bottled water.

All participants are required to fast for the indicated periods before and after dosing as follows:

- Day 1, Morning dose: at least 8h before and 4h after the morning dose
- Day 1, Evening dose: at least 2h before and 1h after the evening dose

- Days 2-6, Both morning and evening doses: at least 2h before and 1h after each dose
- Day 7, Morning dose: at least 2h before and 1h after the morning dose
- Day 7, Evening dose: at least 8h before and 4h after the evening dose

Fluids will be allowed during fasting except for at least 1h before and 1h after each scheduled dose.

The meal schedule will be structured to restrict meals before and after each dose as required. Standard meals will be provided at appropriate times before and after each drug administration and the time the last meal was consumed before and after each dose on Days 1 to 7 will be recorded.

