8.5.7 Serious Adverse Event Reporting

Investigator Reporting of SAEs

All SAEs will be recorded on the appropriate SAE form and sent to DMID Pharmacovigilance Group (PVG). The SAE form will collect all relevant data concerning the SAE, including event term or description, date of study product administration, date of onset, duration or date of resolution, severity, seriousness, outcome, any action taken with the study product, and relationship to each study product or an alternate etiology as assessed by those with the training and authority to make a diagnosis and listed on the Form FDA 1572 (PI, co-investigator, licensed clinicians). In addition, the investigator should provide relevant MH, ConMeds, laboratory or diagnostic results, details of any treatment for the SAE, and a narrative including all other pertinent medical information.

Any AE that meets a protocol-defined serious criterion must be submitted immediately (within 24 hours of site awareness) on an SAE form to the DMID PVG via fax or email. SAEs reported via the SAE Hot Line must be followed with a fax or email submission:

DMID Pharmacovigilance Group
Clinical Research Operations and Management Support (CROMS)
[name]
[name]
SAE Hot Line: [name] (US) or [name] (outside US)
SAE [contact] (US) or [name] (outside US)
SAE Email Address: [contact]

In addition to the SAE form, select SAE data fields must also be entered into the SDCC system. Please see the protocol-specific MOP for details regarding this procedure.

Other supporting documentation of the event may be requested by the DMID PVG and should be provided as soon as possible.

At any time after completion of the study, if the site PI or appropriate sub-investigator becomes aware of an SAE that is suspected to be related to study product, the site PI or appropriate sub-investigator will report the event to the DMID PVG.

Regulatory Reporting of SUSARs

The sponsor will report any Suspected Unexpected Serious Adverse Reactions (SUSAR) to the FDA in an IND safety report. DMID will report an AE as a suspected unexpected adverse event only if there is evidence to suggest a causal relationship between the study intervention and the AE.

The Sponsor must ensure the event meets all three of the definitions:

1. Suspected adverse reaction.
2. Serious.
3. Unexpected.

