#### Interim Safety Analyses

Interim safety analysis is not planned. Safety data may be summarized for *ad hoc* review as requested by the SMC. Top level safety parameters will be assessed between cohorts as needed.

After one participant experienced a moderate allergic reaction, further dosing was discontinued in four participants. As a result, four replacement participants were added at the advice of the SMC. One of these replacement participants also had a moderate allergic reaction to the study product. After meeting a halting rule criterion, the study was halted, and the SMC reviewed data of the two participants who reported a moderate allergic reaction. Under the advisement of the SMC, the study will not proceed with Cohort 2 and Cohort 3.

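### Pregnancy reporting stops at Day 28, but participants must avoid pregnancy until at least Day 37, leaving up to 9 days with no duty to report a pregnancy

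*Protocol*

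**What the plan says.** Protocol 8.5.10 states that pregnancy is not an adverse event. It requires a report to the sponsor of "any pregnancy that occurs during study participation (through study Day 28", with follow-up to pregnancy and newborn outcome and no in-person visit.

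The period in which pregnancy is to be avoided is set elsewhere, and it is longer:

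- Protocol 5.1, criterion 6, Note 4 (women of childbearing potential): contraception "until at least 30 days following receipt of the last dose of study product".
- Protocol 5.1, criterion 8, Note 1 (men): contraception "for at least 30 days after ending study dosing".
- Protocol 1.2, footnote (v), on discharge counselling: "participants must be counseled to use recommended contraception and avoid pregnancy for at least 30 days after the last study dose".

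Protocol 8.4 places "the last dose in the evening of Day 7". Protocol 5.2.1 gives the reason for caution: "Because the effects on the fetus are not known".

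After the study ends, Protocol 8.5.7 requires a report if the investigator "becomes aware of an SAE that is suspected to be related to study product". SAP 9.5 lists pregnancy reports for pregnancies after dosing. It sets no end date and creates no duty to collect them.

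**The concern.** The contraception period is the protocol's own statement of how long after dosing a pregnancy should be avoided. Reporting stops before that period ends, and the protocol gives no reason for the difference. A participant who conceives in the last part of the period has gone against the advice given, yet the site has no duty to report the pregnancy or learn its outcome. For a drug whose fetal effects are unknown, those are cases the sponsor would want to hear about. What is at stake is completeness of safety capture, not any estimate or comparison.

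**Working it through.** **Inputs**

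- End of pregnancy reporting: Day 28 (Protocol 8.5.10).
- Last planned dose: evening of Day 7 (Protocol 8.4).
- Contraception period: at least 30 days after the last dose (Protocol 5.1 and 1.2).
- Outpatient follow-up after the last dose: up to 21 days (Protocol 1.1, Participant Duration).

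**The plan's own figure.** Day 28 − Day 7 = 21 days, which matches the stated follow-up.

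**The gap.** For a last dose on Day *d*, the contraception period ends on Day *d* + 30 at the earliest. The gap after Day 28 is (*d* + 30) − 28 = *d* + 2 days.

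| Last dose | Contraception ends | Gap |
|---|---|---|
| Day 7 (completed) | Day 37 | 9 days |
| Day 6 | Day 36 | 8 days |
| Day 1 | Day 31 | 3 days |

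The shorter gaps are relevant because the SAP's Interim Safety Analyses text (6.2) says "further dosing was discontinued in four participants". If reporting closed at the actual final visit (Day 28 ± 2) instead, the gap after completed dosing would be 37 − 30 = 7 to 37 − 26 = 11 days.

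**Does another clause close it?**

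- Protocol 8.5.7 covers suspected-related SAEs after the study. Under 8.5.2 a congenital anomaly is an SAE, so one that the site later learned of and suspected to be related would be reportable. The pregnancy itself would not be, because 8.5.10 says it is not an AE.
- Protocol 8.6.2 collects unanticipated problems only to the end of the study.
- SAP 9.5 governs display of reports received.

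None of these extends the duty to report a pregnancy past Day 28.

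**Expected number of events.** Protocol 5 allows a male/female ratio as low as 3/5 on active drug and 1/3 on placebo. That is at most 5 of 8 plus 3 of 4, or 8 women per cohort and 24 over three cohorts. Assume all are of childbearing potential and contraceptive failure is 1 to 15% per year (not in the documents). Expected pregnancies = women × annual rate × 9/365.

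- Planned 36 participants: 24 × 0.01 × 9/365 = 0.006 to 24 × 0.15 × 9/365 = 0.089.
- One cohort of 12: 8 × 0.01 × 9/365 = 0.002 to 8 × 0.15 × 9/365 = 0.030.
- Women on active drug in one cohort: 5 × 0.01 × 9/365 = 0.001 to 5 × 0.15 × 9/365 = 0.018.

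The SAP also says four replacements were added, so Cohort 1 may have reached 12 + 4 = 16. If all four were women, the upper figure becomes 12 × 0.15 × 9/365 = 0.044. Partners of male participants are not counted.

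**The case against.** The two windows serve different purposes. The 30-day rule is precautionary conduct for participants, while Day 28 is the end of participation and matches the end of collection for AEs, SAEs, AESIs and unanticipated problems. Nothing requires the windows to be equal. The dosing week and the following 21 days are covered, with follow-up to outcome. The documents give no half-life, so it is not shown that a conception on Days 29 to 37 would involve any drug exposure. The event counts above are ceilings, since women up to 65, including post-menopausal and sterilised women, are eligible. Criterion 8 is weaker support than criterion 6, because 8.5.10 does not expressly mention partner pregnancies even before Day 28. The remedy is passive: a conception after Day 28 cannot be known at the Day 28 call, and no pregnancy test is scheduled after Day −1. The consent form was not available for this review and may already tell participants to report a later pregnancy. Finally, no further cohort will be enrolled.

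These points stand, and they set the priority low. They do not remove the mismatch. The protocol itself judged 30 days to be the period worth guarding, and a reporting window that ends earlier is not explained.

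**Conclusion.** The concern holds. When dosing is completed, 9 of the 30 post-dose days (30%) carry an instruction to avoid pregnancy but no duty to report or follow one; with a last dose on Days 1 to 6 the gap is 3 to 8 days. The day counts rest only on the protocol's text, and because the wording is at least 30 days, Day 37 is the earliest end. They take Day 28 literally as the close of reporting. The event figures rest on the assumed failure rate and on the largest number of women allowed. On any of these assumptions the expected count is well below one. The primary safety, tolerability and PK analyses do not change, and with the study stopped after Cohort 1 the practical effect is minor. The main value is for any participant still within 30 days of the last dose, or for a later SLV213 protocol that reuses this wording.

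**What to change.** Reword Protocol 8.5.10 so that any pregnancy from the first dose through at least 30 days after the last dose is reported, with the outcome follow-up already described there. At the Day 28 call, where the Schedule of Assessments already has counselling, add one sentence asking participants to tell the site of a later pregnancy. This would also help with a conception shortly before Day 28 that has not yet been recognised.

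The cost is one change of wording and one sentence on an existing call, with no added visit, test or blood draw. The drawback is that up to 9 days after the last scheduled contact would depend on the participant calling the site.

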8.6 Unanticipated Problems

8.6.1 Definition of Unanticipated Problems

The Department of Health and Human Services Office for Human Research Protections (DHHS-OHRP) considers **unanticipated problems** involving risks to participants or others to include, in general, any incident, experience, or outcome that meets all of the following criteria:

- Unexpected in terms of nature, severity, or frequency given (a) the research procedures that are described in the protocol-related documents, such as the IRB-approved research

protocol and informed consent document; and (b) the characteristics of the participant population being studied; **and**

- Related or possibly related to participation in the research (“possibly related” means there is a reasonable possibility that the incident, experience, or outcome may have been caused by the procedures involved in the research); **and**
- Suggests that the research places participants or others at a greater risk of harm (including physical, psychological, economic, or social harm) than was previously known or recognized.

Incidents arising from noncompliance with study procedures should be reported as protocol deviations (see [Section 10.1.10](#)). An incident that qualifies as both a unanticipated problems and a protocol deviation should be reported as both.

8.6.2 Unanticipated Problem Reporting

The investigator will report unanticipated problems to the study sponsor (DMID), the reviewing IRB and to the SDCC. The unanticipated problems report will include the following information:

- Protocol identifying information: protocol title and number, PI’s name, and the IRB project number;
- A detailed description of the event, incident, experience, or outcome;
- An explanation of the basis for determining that the event, incident, experience, or outcome represents an unanticipated problem;
- A description of any changes to the protocol or other corrective actions that have been taken or are proposed in response to the unanticipated problem.

To satisfy the requirement for prompt reporting, unanticipated problems will be reported using the following timeline:

- Unanticipated problems that are SAEs will be reported to the IRB and to the SDCC/study sponsor within 24 hours of the investigator becoming aware of the event.
- Any other unanticipated problem will be reported to the IRB and to the SDCC/study sponsor within a timeline defined according to the relevant policies.
- Unanticipated problems, whether they are SAEs or not, will be collected from Day 1 through the end of the study.

8.6.3 Reporting Unanticipated Problems to Participants

Participants will be informed of any unanticipated problems that will potentially influence their participation in this trial.

9. STATISTICAL CONSIDERATIONS

9.1 Statistical Hypotheses

The objectives of the study are to obtain safety data and plasma PK data for 3 escalating doses of SLV213 administered PO daily Q12h for seven days. There are no formal hypotheses being tested in this Phase 1 trial.

9.2 Sample Size Determination

The sample size chosen of a total of 36 is considered to be sufficient for evaluation of safety, tolerability, and PK data of each cohort; the sample size was not based on statistical power considerations.

9.3 Statistical Analyses

9.3.1 General Methodology

A Statistical Analysis Plan (SAP) will be developed and approved by the study biostatistician and investigative team before unblinding, and the database is locked. The SAP will present the detailed statistical methodology to analyze the safety, tolerability, and pharmacokinetic data from this trial. The SAP will also provide details for handling missing data and possible confounding variables.

The safety set will be the primary population for safety data analysis. Analysis of primary and secondary endpoints will be done for each dose of SLV213 and compared with a pooled placebo group from all cohorts. The primary endpoint is the proportion of participants experiencing any TEAEs judged related to study drug vs. placebo. Frequencies and percentages of these events will be presented by treatment group. We will also estimate the event risks by treatment group and risk differences with 95% exact confidence intervals. Risk differences will be estimated for each dose level as compared against the pooled placebo group.

Secondary endpoints:

Binary endpoints will be analyzed using the same methods as described above for the primary endpoint.

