The proposed study will evaluate the safety, tolerability, and pharmacokinetics (PK) of multiple ascending doses (MAD) of SLV213 in healthy male and female participants, 18-65 years of age. This study will help to select the most likely suitable dose (e.g., at Maximum Tolerated Dose [MTD]) for the treatment of patients with COVID-19 in a pivotal study. This double blind, placebo-controlled study will consist of three sequential cohorts of 12 participants each (8 SLV213 and 4 placebo), at doses of 400 mg every 12 hours (Q12h), 600 mg Q12h, and 800 mg Q12h administered orally (PO) for 7 days. After each cohort, a Safety Review Committee (SRC) will evaluate the safety of the regimen before proceeding to dose the next cohort.

Randomization will occur into the respective cohorts as above. Upon meeting the Inclusion/Exclusion criteria, subjects will begin treatment with SLV213 or placebo per their assigned cohort. Participants will take their study drug in the fasted state prior to morning and evening meals and will remain as in-patient in the clinical trial unit (CTU) during all treatments and for approximately 48 hours (h) after the last dose for monitoring. After discharge from the CTU, participants will be monitored by CTU staff by telephone to assess for new adverse events (AEs) and use of concomitant medications (ConMeds) since the last visit or contact, approximately

weekly for three weeks. Participants will be asked to return to the CTU for further assessment of moderate or severe AEs. (For further information on study drug administration see [Section 6.1.2](#). List of assessments from Screening to last study visit can be found in the Schedule of Assessments (SOA), [Section 1.2](#), and in [Section 8.1](#) and [Section 8.3](#)).

Objectives

- Primary: To evaluate the safety and tolerability of multiple ascending doses of SLV213 for 7 days in healthy participants.
- Secondary: To characterize the multiple dose PK of SLV213 in healthy participants.

Outcomes / Endpoints

- Primary:
 - Safety: Type, incidence, severity, and relatedness to study drug of all treatment-emergent systemic, laboratory and electrocardiographic (ECG) adverse events (AEs) and serious adverse events (SAEs) in each treatment cohort from the first dose (Day 1) through the last visit (Day 28 ± 2 days).
 - Tolerability: Proportion of participants experiencing any treatment-emergent AEs assessed as related to study drug vs. placebo.

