3. OBJECTIVES AND ENDPOINTS

OBJECTIVE	ENDPOINTS (OUTCOME MEASURES)
Primary	
Primary
 
To evaluate the safety and tolerability of multiple ascending doses SLV213 for 7 days in healthy participants.
 
Safety: Type, incidence, severity, and relatedness to study drug of all treatment-emergent systemic, laboratory and electrocardiographic (ECG) adverse events (AEs) and serious adverse events (SAEs) in each treatment cohort from the first dose (Day 1) through the last visit (Day 28 ± 2 days).
 
Tolerability: Summarized by dose cohort and include:
 
 Number (and percentage) of participants who: 
 Terminate early or are withdrawn due to treatment-emergent AEs assessed as related to intake of study medication. Have at least 1 treatment-emergent adverse event (TEAE), total and per dose level. Meet Grade 3 abnormal criteria for safety laboratory tests at least once post-dose. Meet Grade 3 abnormal criteria for vital sign measurements at least once post-dose. Meet Grade 3 criteria for safety electrocardiogram (ECG) parameters at least once post-dose. Proportion of oral medication doses completed.
Secondary	
Secondary
 
To characterize the multiple dose pharmacokinetics (PK) of SLV213 in healthy participants.
 
The following single-dose plasma PK parameters will be computed (if estimable) from the plasma total concentration-time data over the 12-hour period following the morning dose on Day 1 for each cohort:
 
 C_{max}: Observed maximum concentration T_{max}: Time of maximum concentration (h) C_{min}: Observed minimum concentration at the end of the dosing interval $AUC_{(0-t)}$: Area under the plasma concentration - time curve (AUC) to the last time with a concentration greater than or equal to the validated limit of quantitation of the assay $AUC_{(0-\infty)}$: Area under the plasma concentration-time curve to infinity $AUC_{(0-12)}$: Area under the plasma concentration - time curve from 0h (pre-dose) to 12 h after dosing

OBJECTIVE	ENDPOINTS (OUTCOME MEASURES)

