9.3.2 Timing of Analyses

The primary clinical database for this study will consist of safety data including unsolicited events, and abnormal laboratory values, as well as baseline/demographic data. Once the last participant has completed the final visit, the primary clinical database will be cleaned, monitored, and locked. After clinical database lock and receipt of secondary endpoint data, a set of topline tables will be generated, including summaries of clinical safety and secondary PK data. The topline report will be made available to the study team for planning subsequent trials and may be presented in a public forum or used for publication in collaboration with the lead PI. These analyses will be considered final and will be included in the Clinical Study Report.

A formal SAP, which will elaborate on the analyses described here and describe any changes to the planned analyses, will be developed and finalized before performing any of these analyses (with the exception of SRC/SMC reviews of descriptive safety analyses).

Interim Analysis

Blinded safety and tolerability data will be periodically reviewed by DMID and the site PI or authorized study clinician (listed on FDA Form 1572) to assess whether rules for halting progression to the next study cohort have been met. An *ad hoc* SMC meeting will review safety data if halting criteria have been met. The SMC will receive data in aggregate. The SMC may request to receive data by study product vs. placebo in a closed session. The SMC may also request that the blind be broken for individual participants, as needed, to assess safety issues. The SMC will be asked to recommend or modification only when there is clear and substantial evidence of a treatment difference. More details about the interim analyses are described below, as well as in a separate guidance document for the SMC.

Interim Safety Analyses

Interim safety analysis is not planned. Safety data may be summarized for ad hoc review as requested by the SMC. Top level safety parameters will be assessed between cohorts as needed.

Interim Pharmacokinetics, Pharmacodynamic, Microbiological Activity, or Efficacy Review

An interim PK and pharmacodynamics (PD) analysis is not planned. If concentration versus time or PK data are available, top-level concentration versus time curves or PK parameters will be assessed between cohorts as needed.

Final Analyses

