Tolerability to study product will be summarized by dose cohort and include number and proportion of participants with early study withdrawal or termination experiencing any AEs assessed as related to study drug vs. placebo as follows: (A) Number and percentage of participants who: (1) Terminate early or are withdrawn due to treatment-emergent AEs assessed as related to intake of study medication; (2) Have at least 1 TEAE, total and per dose level; (3) Meet Grade 3 abnormal criteria for safety laboratory tests at least once post-dose; (4) Meet Grade 3 abnormal criteria for VS measurements at least once post-dose; and (5) Meet Grade 3 criteria for safety ECG parameters at least once post-dose, and (B) Number and percentage of oral medication doses completed.

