### 3. STUDY OBJECTIVES AND ENDPOINTS

OBJECTIVE	ENDPOINTS (OUTCOME MEASURES)
Primary To evaluate the safety and tolerability of multiple ascending doses SLV213 for 7 days in healthy participants.	Primary Safety: Type, incidence, severity, and relatedness to study drug of all treatment-emergent systemic, laboratory and electrocardiographic (ECG) adverse events (AEs) and serious adverse events (SAEs) in each treatment cohort from the first dose (Day 1) through the last visit (Day 28 ± 2 days). Tolerability: Summarized by dose cohort and include: 
 
• Number (and percentage) of participants who:           
 
1) Terminate early or are withdrawn due to treatment-emergent AEs assessed as related to intake of study medication.
 
2) Have at least 1 treatment-emergent adverse event (TEAE), total and per dose level.
 
3) Meet Grade 3 abnormal criteria for safety laboratory tests at least once post-dose.
 
4) Meet Grade 3 abnormal criteria for vital sign measurements at least once post-dose.
 
5) Meet Grade 3 criteria for safety electrocardiogram (ECG) parameters at least once post-dose.
 
 
 
• Proportion of oral medication doses completed.
 

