## 6. GENERAL STATISTICAL CONSIDERATIONS

### 6.1. General Principles

All continuous variables will be summarized using the following descriptive statistics: n (non-missing sample size), mean, standard deviation, median, maximum, and minimum. The frequency and percentages (based on analysis population sample size, unless otherwise stated) of observed levels will be reported for all categorical measures. In general, all data will be listed, sorted by treatment group, participant, parameter, and time point as applicable.

The Safety Population will be the primary population used for summaries of safety endpoints. The PK Analysis Population will be used for summaries of PK endpoints. Analyses of primary and secondary endpoints will be done for each dose of SLV213 and compared with a placebo group.

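### The SAP drops, without saying so, the risk difference and exact intervals that the protocol promises for related TEAEs, and it replaces the proportion of doses completed with a count of full completers

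*Protocol*

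**What the plan says.** **Related TEAEs, protocol.** Section 9.3.1 states: "The primary endpoint is the proportion of participants experiencing any TEAEs judged related to study drug vs. placebo". It then says "We will also estimate the event risks by treatment group and risk differences with 95% exact confidence intervals", with each dose level set against pooled placebo. The synopsis (1.1) gives the same quantity as the primary tolerability outcome: "Proportion of participants experiencing any treatment-emergent AEs assessed as related to study drug vs. placebo". The endpoint table in protocol Section 3 does not list that proportion. Its nearest tolerability item covers TEAEs of any cause: "Have at least 1 treatment-emergent adverse event (TEAE), total and per dose level". SAP Section 3 repeats that table.

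**Related TEAEs, SAP.** Section 6.1 keeps the comparison in words only: "Analyses of primary and secondary endpoints will be done for each dose of SLV213 and compared with a placebo group". Section 9.3 specifies one interval method, one-sample Clopper-Pearson, for Table 24.

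**Doses.** Protocol 9.3.6 asks for "Number and percentage of oral medication doses completed", and SAP Section 3 lists "Proportion of oral medication doses completed". SAP 9.9.2 and the last row of Table 14 instead count participants who completed all their doses. The Table 14 footnote confirms that n is a number of participants.

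**Declaring changes.** Protocol 9.3.2 says the SAP will "describe any changes to the planned analyses". SAP Section 15 records that enrolment ended after Cohort 1 and that the shells serve an abbreviated study report on the 400 mg and placebo groups.

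**The concern.** A report that follows the SAP would contain no estimate of the drug-placebo difference that protocol 9.3.1 calls primary, and no statement of its precision. A reader would have to rebuild it from the Table 22 counts. The listed doses endpoint would have no summary at all and would have to be assembled from Listings 1 and 8.

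Both quantities bear on what happened in this trial. SAP 6.2 describes two moderate allergic reactions, dosing discontinued in four participants, four replacements added, and a decision not to open Cohorts 2 and 3. How much more often related events occurred on 400 mg than on placebo, and how much drug participants took, are the obvious questions for the report. A completer count treats a participant stopped after one dose the same as one stopped after 13.

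**Working it through.** **1. What each document provides**

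| Quantity | Protocol | SAP |
|---|---|---|
| Related TEAE risk per group | 9.3.1 | Tables 22 and 25: n and % (Figures 9 and 10 show related events by SOC) |
| Exact 95% CI on that risk | 9.3.1 | None. Table 24 has Clopper-Pearson CIs for any-cause TEAEs, including its overall row |
| Risk difference vs placebo with exact 95% CI | 9.3.1 | None in any section or shell |
| Doses completed, number and % | 9.3.6 | Listed in Section 3. 9.9.2 and Table 14 count participants, largely repeating the all-planned-doses row of Table 10 |
| Declaration of changes | 9.3.2 | Section 15: end of enrolment and abbreviated report only |

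**2. The plan's own figure.** The only stated design number is N = 36, not based on power. It reproduces: 3 cohorts × (8 active + 4 placebo) = 36. SAP Table 4 shows a different split (6 + 6 + 6 + 18, also 36). I use 8 and 4 per cohort, as in protocol 4.1 and SAP Section 5.

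**3. Can the missing estimate still be computed?** Yes. One active dose and one placebo group remain.

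*Inputs.* Planned Cohort 1 is 8 vs 4. SAP 6.2 adds four replacements, and SAP 6.3.3 keeps replaced and replacement participants in the Safety population once dosed, so it could reach 12 + 4 = 16. The documents give neither the arm split of the 16 nor event counts by arm. I assume 4 events on active and 1 on placebo and vary the split.

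*Method.* For each candidate difference d, the score statistic is T = (p1 − p0 − d) / √(q1(1 − q1)/n1 + q0(1 − q0)/n0). Here p1 and p0 are the observed risks, and q1 and q0 are the maximum-likelihood risks constrained to q1 − q0 = d. Each one-sided p-value is the largest exact binomial tail probability over the nuisance risk. The interval keeps every d for which both p-values exceed 0.025, searched in steps of 0.005.

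| Active | Placebo | Difference (points) | Exact 95% CI (points) |
|---|---|---|---|
| 4/8 (as planned) | 1/4 | 50.0 − 25.0 = +25.0 | −39.5 to +71.0 |
| 4/12 | 1/4 | 33.3 − 25.0 = +8.3 | −49.0 to +51.0 |
| 4/11 | 1/5 | 36.4 − 20.0 = +16.4 | −40.5 to +57.0 |
| 4/10 | 1/6 | 40.0 − 16.7 = +23.3 | −29.0 to +64.0 |
| 4/9 | 1/7 | 44.4 − 14.3 = +30.2 | −19.5 to +70.0 |
| 4/8 | 1/8 | 50.0 − 12.5 = +37.5 | −11.0 to +75.5 |

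The per-group Clopper-Pearson intervals are equally simple: 4/11 gives 10.9% to 69.2%, and 1/5 gives 0.5% to 71.6%.

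**4. Do the two dose measures agree?** Each participant is due 7 days × 2 = 14 doses. Assume 8 + 3 = 11 dosed on active, where 3 originals stopped and were replaced and one replacement also stopped. Four then stopped and 7 completed.

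- Planned doses: 11 × 14 = 154.
- All four stop after dose 1: (7 × 14 + 4 × 1)/154 = 102/154 = 66.2%.
- All four stop after dose 13: (7 × 14 + 4 × 13)/154 = 150/154 = 97.4%.
- Completers in both cases: 7/11 = 63.6%.

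The Table 14 figure is identical in two situations about 31 points apart (97.4 − 66.2 = 31.2).

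**The case against.** The strongest reply is that little is lost.

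- **The promised contrast has changed.** It used placebo pooled over all cohorts (3 × 4 = 12), and Cohorts 2 and 3 were never enrolled. That is right: only a reduced version is available. It is still one dose against placebo and still computable.
- **The study is small and descriptive.** There are no hypotheses and no power basis, and every illustrative interval above includes zero and spans roughly 87 to 111 points. That could be a reason to drop the estimate, but the SAP does not give it. An interval is estimation, not testing, and here its purpose is to show the imprecision.
- **Section 15 announces an abbreviated report, and the Section 3 safety endpoint covers relatedness.** Both are true, and related events are reported per group as n and %. Neither text names the dropped difference, the dropped intervals or the changed doses measure.
- **Listings 1, 2 and 8 show each dose given, each discontinuation and each missed dose.** They do, and at this size they show individual patterns better than a pooled proportion. A listing is still not the summary of a listed endpoint.
- **The 8 vs 8 split is unlikely.** I agree. It needs all four replacements on placebo, while SAP 4.1 attributes the halting to the 400 mg group and one replacement reacted. It marks only the far end of the assumed range.

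The protocol asks only for an exact interval. The unconditional method is my choice, and another exact method would serve if it is named.

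**Conclusion.** The concern holds. Followed as written, the SAP omits the risk difference and the intervals that protocol 9.3.1 attaches to its stated primary endpoint, and it summarises a different quantity from the doses endpoint in its own Section 3. Neither departure is declared, and the stop after Cohort 1 makes neither quantity impossible to report.

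These textual findings need no assumptions. The sizes do, because event counts, arm split and stopping times are not given. Under the assumed 4 vs 1 events, the difference runs from +8 to +38 points across the possible splits, with very wide intervals. Under the assumed 7 of 11 completers, dose completion runs from 66% to 97%.

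This should be fixed but does not threaten the trial. It affects completeness of reporting and traceability to the protocol, not participant protection.

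**What to change.** Make these changes as a SAP addendum, which Section 15 allows before final data lock. After lock, provide the analyses and the explanation in the study report.

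1. **SAP 9.3 and Table 22.** In the row for at least one related adverse event, add exact 95% CIs per group. Add the 400 mg minus placebo risk difference with an exact 95% CI (unconditional suggested) and name the method. Use actual Safety-population denominators, including dosed replacements.
2. **SAP 9.9.2 and Table 14.** Add doses taken over doses planned (14 per participant), as number and percentage per group. Keep the completer count beside it.
3. **SAP Section 15.** Note that protocol Section 3 and protocol 9.3.1 differ on the primary endpoint and say which is followed. List, with reasons, any intended departure from 9.3.1 or 9.3.6, including that pooled placebo now means Cohort 1 placebo only.

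The cost is some SAP wording and a few table cells, with no new data. The reported difference will look imprecise, because it is.
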